7.4.1. Pre-Titration Tolerability Assessment Requirements

Tolerability of investigational product must be assessed prior to titrating a subject to a higher dose. A review of adverse events and safety laboratory results (eg, chemistry, hematology, and coagulation) obtained within 2 months of the up-titration visit must be performed as part of the investigational product tolerability assessment, prior to any planned up-titration in study medication (eg, Month 3, Month 6). Safety laboratory results obtained at the Month 1 visit (for titration at Month 3) or at the 1 Month Post-Titration Assessment visit (for titration prior to or at the subsequent quarterly visit) are acceptable for review purposes; however, if for any reason, laboratory results are not available at the time of the planned up-titration visit, additional laboratory samples must be obtained and reviewed, prior to up-titrating the subject to a higher dose.

To be eligible for a dose up-titration:

- Subjects should not be experiencing significant AEs that are suspected to be related to investigational product (eg, severe pruritus) or displaying other symptoms that may indicate intolerability of investigational product.
- There must be no clinically significant increase (as determined by the investigator) in the subject's liver function tests. Subjects whose total bilirubin is $>2\times$ baseline (and $>ULN$) cannot be up-titrated, and additional unscheduled safety visit procedures, outlined in [Section 9.7.19](#), should be implemented, as required.

7.4.2. Safety Criteria for Adjustment or Stopping Doses

Investigational product may be temporarily decreased (eg, from 10 mg to 5 mg daily, or by decreasing dosing frequency) or temporarily or permanently stopped based on tolerability

concerns. The dose of investigational product should be resumed to the maintenance dose in a blinded manner once the issues relating to the lack of tolerability are resolved.

Subjects that discontinue investigational product are expected to continue in the study (and follow the regular visit schedule) until the end of the study, and the study will only terminate at the time when the needed number of adjudicated events has accrued. If a subject reaches an event, he or she should continue the regular visit schedule and continue taking investigational product as long as the Investigator assesses it as safe. In general, subjects should be strongly encouraged to both stay on investigational product and remain in the study until study termination.

7.5. Criteria for Study Termination

The Sponsor reserves the right to terminate the study at any time. It is normal procedure to review the emerging clinical and safety data. As a result of such a review or a recommendation by the DMC, it may be necessary to stop the study before all events have been accrued, and when subjects are still active on the study. In addition, the Sponsor may terminate the study at an investigational site at any time (eg, poorly performing sites, as determined by the number of subjects enrolled or the quality of the study data).

The Investigator and/or Sponsor (or designee) must notify the Institutional Review Board/Independent Ethics Committee (IRB/IEC) of discontinuation of a site or the study and the reason for doing so.

Investigators will be informed by the Sponsor as to when the final study visit is to be completed, and should then schedule all subjects for the End of Study Visit. The window of time for scheduling the visit will be based on a final projection of when the requisite 127 adjudicated events will have been accrued.

8. SELECTION AND WITHDRAWAL OF SUBJECTS

8.1. Subject Population

This study will be conducted at approximately 170 international study sites with experience in treating patients with PBC. Prospective subjects will be identified primarily from the hospital and/or physician's database of patients with PBC, or may be referred from other physicians. Patients may self-refer to an Investigator if they become aware of the study through local, national, or international PBC patient societies, forums, or networks.

8.2. Subject Inclusion Criteria

1. Definite or probable PBC diagnosis (consistent with AASLD and EASL practice guidelines; [Lindor 2009](#); [EASL 2009](#)), as demonstrated by the presence of ≥ 2 of the following 3 diagnostic factors:
 - History of elevated ALP levels for at least 6 months.
 - Positive antimitochondrial antibody (AMA) titer or if AMA negative or in low titer (<1:80) PBC-specific antibodies (anti-GP210 and/or anti-SP100 and/or antibodies

against the major M2 components [PDC-E2, 2-oxo-glutaric acid dehydrogenase complex]).

- Liver biopsy consistent with PBC.
2. A mean total bilirubin $>ULN$ and $\leq 5 \times ULN$ and/or a mean ALP $>3 \times ULN$
 3. Age ≥ 18 years
 4. Either is not taking UDCA (no UDCA dose in the past 3 months) or has been taking UDCA for at least 12 months with a stable dose for ≥ 3 months prior to Day 0.
 5. Contraception: Female subjects of child-bearing potential must use ≥ 1 effective method of contraception during the study and until 30 days following the last dose of investigational product. Effective methods of contraception are considered to be those listed below:
 - Barrier method, ie, (a) condom (male or female) or (b) diaphragm, with spermicide
 - Intrauterine device (IUD)
 - Vasectomy (partner)
 - Hormonal (eg, contraceptive pill, patch, intramuscular implant or injection)
 - Abstinence, if in line with the preferred and usual lifestyle of the subject
 6. Must provide written informed consent and agree to comply with the study protocol

8.3. Subject Exclusion Criteria

1. History or presence of other concomitant liver diseases including:
 - Hepatitis C virus infection
 - Active hepatitis B infection; however, subjects who have seroconverted (hepatitis B surface antigen and hepatitis B e antigen negative) may be included in this study after consultation with the Medical Monitor.
 - Primary sclerosing cholangitis
 - Alcoholic liver disease
 - Definite autoimmune liver disease or overlap hepatitis
 - Nonalcoholic steatohepatitis
 - Gilbert's Syndrome
2. Presence of clinical complications of PBC or clinically significant hepatic decompensation, including:
 - History of liver transplant, current placement on a liver transplant list, or current MELD score >12 . Subjects who are placed on a transplant list despite a relatively early disease stage (for example per regional guidelines) may be eligible as long as they do not meet any of the other exclusion criteria.

- Cirrhosis with complications, including history (within the past 12 months) or presence of:
 - Variceal bleed
 - Uncontrolled ascites
 - Encephalopathy
 - Spontaneous bacterial peritonitis
 - Known or suspected hepatocellular carcinoma
 - Prior transjugular intrahepatic portosystemic shunt procedure
 - Hepatorenal syndrome (type I or II) or Screening (visit 1 or 2) serum creatinine >2 mg/dL (178 µmol/L)
3. Mean total bilirubin >5× ULN
 4. Subjects who have undergone gastric bypass procedures (gastric lap band is acceptable) or ileal resection or plan to undergo either of these procedures.
 5. Other medical conditions that may diminish life expectancy, including known cancers (except carcinomas *in situ* or other stable, relatively benign conditions such as chronic lymphatic leukemia).
 6. If female: plans to become pregnant, known pregnancy or a positive urine pregnancy test (confirmed by a positive serum pregnancy test by the central laboratory), or lactating.
 7. Known history of human immunodeficiency virus infection.
 8. Medical conditions that may cause non-hepatic increases in ALP (eg, Paget's disease or fractures within 3 months).
 9. Other clinically significant medical conditions that are not well controlled or for which medication needs are anticipated to change during the study.
 10. History of alcohol abuse or other substance abuse within 1 year prior to Day 0.
 11. Participation in another investigational product, biologic, or medical device study within 30 days prior to Screening. Participation in a previous study of OCA is allowed with 3 months washout prior to enrollment in this study.
 12. Mental instability or incompetence, such that the validity of informed consent or ability to be compliant with the study is uncertain.
 13. History of known or suspected clinically significant hypersensitivity to OCA or any of its components.
 14. UDCA naïve (unless contraindicated)

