- For those subjects that up-titrate to 10 mg, dosing may be decreased to 5 mg at any time during the study as considered clinically appropriate (eg, based on tolerability). Subjects may be titrated back to a maximum dose of 10 mg once daily based on tolerability and clinical judgment of the Investigator.
- Subjects who are cirrhotic and classified as Child-Pugh Class B or Child-Pugh Class C will initiate a modified treatment regimen with 5-mg OCA or matching placebo once weekly for at least 3 months. Subjects classified as Child-Pugh Class B should eventually titrate to a maximum dose of 5-mg OCA or matching placebo once daily, based on tolerability and biochemical response. Subjects classified as Child-Pugh Class C should titrate to a maximum dose and frequency of 10-mg OCA or matching placebo twice weekly, based on tolerability and biochemical response.

Planned Dosing Regimen by Cirrhosis and Child-Pugh Score			
	Planned Dosing Regimen		
	Standard	Modified	
	Non-Cirrhotic/ Child-Pugh A	Child-Pugh B	Child-Pugh C
Starting Dose^a (Day 0)	5 mg daily	5 mg once weekly	5 mg once weekly
Titration 1^b (≥Month 3)	10 mg daily	5 mg twice weekly	5 mg twice weekly
Titration 2^b (≥6 weeks after Titration 1)	NA	10 mg twice weekly	10 mg twice weekly
Titration 3^b (≥6 weeks after Titration 2)	NA	5 mg daily	NA

^a Starting dose based on subject's cirrhosis status and Child-Pugh Score at Screening.

^b Planned titration regimen is shown; however, the titration of dose and/or frequency is dependent on subject tolerability, biochemical response, and/or changes in cirrhosis status or Child-Pugh Score at any time during the study.

Number of Subjects (planned):
Approximately 428 subjects

Diagnosis and Main Criteria for Inclusion:
Inclusion Criteria

- Definite or probable PBC diagnosis (consistent with American Association for the Study of Liver Diseases [AASLD] and the European Association for the Study of the Liver [EASL] practice guidelines; Lindor 2009; EASL 2009), as demonstrated by the presence of ≥2 of the following 3 diagnostic factors:
 - History of elevated ALP levels for at least 6 months
 - Positive antimitochondrial antibody (AMA) titer or if AMA negative or in low titer (<1:80) PBC-specific antibodies (anti-GP210 and/or anti-SP100 and/or antibodies against the major M2 components [PDC-E2, 2-oxo-glutaric acid dehydrogenase complex])
 - Liver biopsy consistent with PBC
- A mean total bilirubin >ULN and ≤5× ULN and/or a mean ALP >3× ULN
- Age ≥18 years

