5. INTRODUCTION

5.1. Overview of Primary Biliary Cirrhosis and Obeticholic Acid

Primary biliary cholangitis, (PBC, also known as primary biliary cirrhosis) is a serious, life-threatening, cholestatic liver disease of unknown etiology that, without treatment, frequently progresses to hepatic fibrosis and eventual cirrhosis, hepatic decompensation, and necessitates liver transplantation or results in death. PBC is a rare disease with reported prevalence in the US of 40.2/100,000 (Kim 2000). PBC disproportionately affects women approximately 10:1 and is typically diagnosed in patients between 40 to 60 years of age.

Ursodeoxycholic acid (UDCA), a physiological constituent of human bile, is currently the only treatment approved for PBC (Lindor 2009). While UDCA therapy has a marked effect on the treatment of PBC, up to 50% of patients show a suboptimal response or no response to UDCA. Such patients are at significantly increased risk of a poor clinical outcome due to PBC disease progression. There is a clear unmet medical need for better therapies for patients with PBC that have an inadequate response to UDCA, or those who cannot tolerate UDCA (typically due to gastrointestinal adverse events [AEs]). Obeticholic acid (OCA) is being developed for the treatment of PBC and to provide patients that have an inadequate response to or poor tolerance of UDCA a novel treatment option that is safe and effective.

OCA is a modified bile acid and farnesoid X receptor (FXR) agonist that is derived from the primary human bile acid chenodeoxycholic acid (CDCA). OCA is currently being developed in the United States (US) and Europe for the treatment of PBC and other chronic liver diseases. OCA has been granted Orphan Drug Designation in the US (09 Apr 2008) and Orphan Medicinal Product Designation in the European Union (EU) (27 Jul 2010) for the treatment of PBC. The United States Food and Drug Administration (FDA) has granted accelerated approval for Ocaliva for the treatment of PBC. Ocaliva is not yet approved outside the United States for use in any indication.

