9. TREATMENT OF SUBJECTS

9.1. Investigational Product Treatment Regimen

The term investigational product refers to either OCA (provided as part of this clinical study) or matching placebo.

Two treatment groups will be evaluated: OCA and placebo. Investigational product will be administered orally. Each dose will be made up of 1 tablet (ie, one 5 mg OCA tablet or one 10 mg OCA tablet, or matching placebo).

Investigational product will be taken orally, up to once daily, for the duration of the study.

All subjects will be instructed to begin dosing on the day after the Day 0 visit (ie, on Day 1) and to take investigational product at approximately the same time of day. Subjects must be instructed to swallow the tablet whole; they must not chew, divide, or crush the tablet.

At each study visit where the daily dose of investigational product is administered at the site, all assessments, except for the post-dose collection of blood samples for the subset of subjects participating in the Month 9 PK assessment, must be completed before administration of investigational product.

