9.2.1. Prohibited Medications

Commercial OCA therapy (if available) is prohibited while on investigational product, and if prescribed during the course of the study, the Investigator should be cognizant of the possibility of double dosing. Subjects who continue with commercial OCA therapy must discontinue study medication and are expected to continue through the end of the study (see [Section 7.4.2](#)). The study will only terminate at the time when the needed number of adjudicated events has accrued or at the discretion of the Sponsor. Subjects will need to complete EOT procedures but continue with regularly scheduled visits until the study is terminated (see [Section 9.7.18](#) Early Discontinuation and/or Early Termination Procedures).

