3. Mean total bilirubin >5x ULN
4. Subjects who have undergone gastric bypass procedures (gastric lap band is acceptable) or ileal resection or plan to undergo either of these procedures
5. Other medical conditions that may diminish life expectancy, including known cancers (except carcinomas in situ or other stable, relatively benign conditions such as chronic lymphatic leukemia)
6. If female: plans to become pregnant, known pregnancy or a positive urine pregnancy test (confirmed by a positive serum pregnancy test), or lactating
7. Known history of human immunodeficiency virus infection
8. Medical conditions that may cause nonhepatic increases in ALP (eg, Paget's disease or fractures within 3 months)
9. Other clinically significant medical conditions that are not well controlled or for which medication needs are anticipated to change during the study
10. History of alcohol abuse or other substance abuse within 1 year prior to Day 0
11. Participation in another investigational product, biologic, or medical device study within 30 days prior to Screening. Participation in a previous study of OCA is allowed with 3-month washout prior to enrollment in this study
12. Mental instability or incompetence, such that the validity of informed consent or ability to be compliant with the study is uncertain
13. History of known or suspected clinically significant hypersensitivity to OCA or any of its components
14. UDCA naïve (unless contraindicated)

Investigational Product, Dosage and Mode of Administration: OCA (5 mg or 10 mg tablets)	
Reference Therapy, Dosage and Mode of Administration: Placebo (matching tablets)	
Duration of Treatment: It is expected that subjects will be followed up for a minimum of 6 years. The study is event driven and total duration of treatment will be determined by the time to accrue 127 total primary endpoint events.	
Criteria for Evaluation:	
Primary Objectives	Assessments
Clinical outcomes	
 • Death (all-cause) • Liver transplant • MELD score ≥ 15 • Hospitalization (as defined by a stay of 24 hours or greater) for new onset or recurrence of: 
 – Variceal bleed – Hepatic encephalopathy (as defined by a West Haven score of ≥ 2) – Spontaneous bacterial peritonitis (confirmed by diagnostic paracentesis) • Uncontrolled ascites (diuretic-resistant ascites requiring therapeutic paracentesis at a frequency of at least twice in a month)
Secondary Objectives	

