5. INTRODUCTION

5.1. Overview of Primary Biliary Cholangitis and Obeticholic Acid

Primary biliary cholangitis, (PBC, also known as primary biliary cirrhosis [[Beuers 2015a](#), [Beuers 2015b](#), [Beuers 2015c](#)]) is a serious, life-threatening, cholestatic liver disease of unknown etiology that, without treatment, frequently progresses to hepatic fibrosis and eventual cirrhosis, hepatic decompensation, and necessitates liver transplantation or results in death. PBC is a rare disease with reported prevalence in the United States (US) of 40.2/100 000 ([Kim 2000](#)). PBC disproportionately affects women approximately 10:1 and is typically diagnosed in patients between 40 to 60 years of age.

Historically, the only approved drug therapy for PBC has been the bile acid, ursodeoxycholic acid (UDCA), a physiological constituent of human bile ([Lindor 2009](#)). While UDCA therapy had a marked effect on the treatment of PBC, up to 50% of patients showed a suboptimal response or no response to UDCA. Such patients were at significantly increased risk of a poor clinical outcome due to PBC disease progression.

Obeticholic acid (OCA), a farnesoid X receptor (FXR) agonist and modified bile acid derived from the primary human bile acid chenodeoxycholic acid (CDCA), was developed for the treatment of PBC and to provide patients who have an inadequate response to or poor tolerance of UDCA a novel treatment option that was safe and effective ([Pellicciari 2002](#)). In May 2016, the US Food and Drug Administration (FDA) granted accelerated approval for OCA (marketed as Ocaliva), for the treatment of patients with PBC in combination with UDCA in adults with an inadequate response to UDCA or as monotherapy in adults unable to tolerate UDCA. In December 2016, the European Commission granted conditional approval for Ocaliva for the same indication.

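### The 3-month OCA washout applies only after a previous OCA study, so a patient on marketed OCA up to Day 0 is eligible and baseline ALP and bilirubin may be measured on drug

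*Protocol*

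**What the plan says.** Version 3.1, Section 8.3, criterion 11 has two clauses. The first excludes participation in another investigational study within 30 days before Screening. The second is the only washout rule for OCA: "Participation in a previous study of OCA is allowed with 3 months washout prior to enrollment in this study". The Version 4 synopsis repeats it: "Participation in a previous study of OCA is allowed with 3-month washout prior to enrollment in this study".

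Marketed OCA appears in Section 9.2.1: "Commercial OCA therapy (if available) is prohibited while on investigational product". Section 9.1 starts investigational product on Day 1, the day after randomization.

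Both versions record that OCA is on the market. Version 3.1, Section 5.1: "The United States Food and Drug Administration (FDA) has granted accelerated approval for Ocaliva for the treatment of PBC". Version 4, Section 5.1 dates the US approval to May 2016 and adds: "In December 2016, the European Commission granted conditional approval for Ocaliva for the same indication". Recruitment is planned over about 4 years (Section 7.1).

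Biochemical entry requires "A mean total bilirubin >ULN and ≤5× ULN and/or a mean ALP >3× ULN", judged on the mean of the screening values (Section 9.7.6).

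Section 9.2 asks for concomitant medications to be stable before Day 0. Under PBC-specific therapy it says that subjects should ideally stay on their baseline PBC treatments during the study unless the investigator no longer finds these appropriate.

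**The concern.** The sponsor judged recent OCA exposure important enough for a 3-month gap, but tied that gap to how the drug was obtained. Carry-over is the same whether the tablets came from a trial or from a pharmacy. UDCA, the other PBC drug, has a time rule regardless of source (inclusion criterion 4: off for 3 months, or on for at least 12 months and stable for at least 3).

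The protocol treats commercial OCA as a threat after randomization. It is a possible source of bias on the placebo arm (Section 5.5.2.3), a reason to stop investigational product (Section 8.4.3) and a loss that the DMC monitors (Section 13.1.12). Use before randomization is not covered.

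At stake is what the baseline means. A patient randomized straight from commercial OCA has a treated baseline. On placebo, that patient shows what happens when OCA is stopped. On OCA, that patient shows continued treatment. Neither is the contrast the primary objective describes, which is OCA against placebo on top of local standard of care.

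**Working it through.** **1. Does any rule exclude a patient stable on marketed OCA?** Going through the 6 inclusion and 14 exclusion criteria of Version 3.1 and the related text:

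| Rule | Reach | Closes the gap? |
|---|---|---|
| Criterion 11, OCA clause | Previous OCA study only | No |
| Criterion 11, 30-day clause | Other investigational studies | No |
| Criterion 9 | Other medical conditions with changing medication needs | No |
| Criterion 13 | Hypersensitivity to OCA | No |
| Section 9.2, stable medication before Day 0 | Met by a patient stable on OCA | No |
| Section 9.2.1 | Only while on investigational product, so from Day 1 | No |

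A site following the text can take both screening samples and the Day 0 sample on commercial OCA, stop it, and randomize.

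**2. Where the pretreatment values go.**
- Eligibility: mean screening ALP and bilirubin (Section 9.7.6).
- Randomization stratum: mean baseline bilirubin above ULN or not (Section 9.4).
- Key secondary endpoints 3 and 4: change from Baseline in bilirubin and ALP by ANCOVA with Baseline as covariate (Section 13.1.4), both in the alpha-controlled sequence of Section 13.1.10.
- Safety thresholds: bilirubin above 2 times baseline (Sections 7.4.1 and 8.4.3.1) and AST or ALT above 3 times baseline (Section 8.4.3.1).

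Every candidate baseline sample precedes Day 1, so each could be on drug, whichever definition of Baseline is used.

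**3. An internal conflict.** For a patient whose baseline PBC therapy is OCA, the Section 9.2 advice to stay on baseline therapy and the Section 9.2.1 prohibition cannot both be followed. The two passages need to be reconciled.

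**4. The washout clock for former trial participants.** Within criterion 11, one clause counts back from Screening and the other from enrollment. Section 9.7.1 puts Screening Visit 1 at 3 to 8 weeks and Screening Visit 2 at 1 to 6 weeks before Day 0. Take 3 months as about 13 weeks and enrollment as Day 0:
- Screening Visit 1: 13 − 8 = 5 weeks to 13 − 3 = 10 weeks after the last dose.
- Screening Visit 2: 13 − 6 = 7 weeks to 13 − 1 = 12 weeks.

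On that reading, a minimally compliant subject has neither eligibility sample a full 3 months off drug.

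**5. What a treated baseline does to the ALP comparison.** Inputs from Study 747-301 (Section 5.4): mean ALP change −5% on placebo and −39% on 10 mg. Set untreated ALP to 100, and assume an average response and full return to the untreated level on stopping.

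| Patient at entry | Baseline | Later, placebo | Later, OCA | Change, placebo | Change, OCA | Contrast |
|---|---|---|---|---|---|---|
| Not on OCA | 100 | 95 | 61 | −5 | −39 | 34 |
| On OCA | 61 | 95 | 61 | +34 | 0 | 34 |

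The absolute contrast between arms is the same. What changes is the baseline itself, each arm's change from it, and what those changes mean.

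**6. Sample size is not in question.** With O'Brien-Fleming-type looks at 50% and 75%, 127 events give about 81% power at HR 0.60, against the stated 80%. Event probabilities of 0.398 and 0.263 average 0.331; 127/0.331 is about 384; with the 10% dropout in the Version 4 synopsis, 384/0.9 is about 427, against 428.

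**The case against.** The documents permit such patients but do not show that any were enrolled, and the share could be near zero. The only movement they anticipate is out of the study towards commercial OCA. Randomization balances recent users across arms in expectation, so this is not in itself bias between arms. An investigator might also read Sections 9.2 and 9.2.1 together as discouraging such enrolment. Recent use can partly be identified already, from PBC treatment history at Screening (Section 12.2.6), medications within 30 days of Screening (Section 9.2) and plasma OCA at Day 0 (Section 9.7.7). The full Version 4 Sections 8 and 9 are not shown. All of this stands and limits the size of the point. It does not close the gap: eligibility is fixed in the protocol, and no analysis plan can restore an untreated baseline.

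A reader might infer three stronger things that the documents do not support.
- *A near-doubled ALP effect.* A return from 61 to 100 is a rise of 1/0.61 − 1 = 64%, which could be set against the 34 points seen in untreated patients. That mixes two denominators and leaves the 5% placebo fall out of one side. On the primary ANCOVA scale of absolute change the contrast is 34 either way. Only the repeat analysis on percentage change would look different, through its smaller denominator.
- *That these patients are known inadequate responders.* No minimum time on OCA is implied, so a patient may have just started. After an average 39% fall, ALP above 3 times ULN means only that untreated ALP was above 3/0.61 = 4.9 times ULN. A patient who qualifies on bilirubin alone may have responded on ALP.
- *A definite loss of power.* This would need both the share of such patients and their hazard ratio. The documents give neither, and setting the hazard ratio to 1 contradicts assuming a full biochemical response in the same patients. Nor would a washout cure it, because prior inadequate responders remain eligible once washed out.

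**Conclusion.** The gap holds for Version 3.1 and, as far as the synopsis shows, for Version 4: a patient on marketed OCA up to Day 0 is eligible. For such a patient the baseline behind eligibility, the bilirubin stratum, two alpha-controlled key secondary endpoints and the baseline-relative safety thresholds is measured on drug, and assignment to placebo is withdrawal of OCA rather than untreated control. The primary comparison may also be diluted, by an amount that cannot be calculated from the documents. The 5-week figure depends on reading enrollment as Day 0, so it shows ambiguous wording rather than a demonstrated error. The point does not extend to a claim of bias between arms, an inflated ALP effect or a stated power loss.

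**What to change.** Reword criterion 11 so that the sponsor's existing 3-month interval covers OCA from any source (previous study, commercial supply or other access) and runs to Screening Visit 1 instead of enrollment. Reconcile the PBC-specific therapy text of Section 9.2 with Section 9.2.1 for patients whose baseline therapy is OCA. Check that the full Version 4 Sections 8.3 and 9.2.1 carry the same wording.

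For subjects already randomized, flag OCA use within 3 months before Screening from the PBC treatment history, prior medications and Day 0 plasma OCA. The medication record reaches back only 30 days before Screening, so the treatment history has to cover the rest of the interval. Repeat the primary analysis and the ALP and bilirubin key secondary analyses without the flagged subjects, as a sensitivity analysis.

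The cost is one sentence in the criteria, a flag built from data already collected and one sensitivity analysis. A few patients on commercial OCA become ineligible or are screened later. The change protects the baselines; it does not exclude patients who responded poorly to OCA in the past.
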